5.5 STRATEGIES FOR RECRUITMENT AND RETENTION

Patients will be recruited from the Severe Asthma Clinics at the University of Michigan. The program currently has 300 patients receiving biologics for asthma. We will also recruit patients from other clinics that are receiving biologics as long as the providers are willing to obtain and document detailed information on biologic response to therapy.

6 STUDY INTERVENTION

6.1 STUDY INTERVENTION(S) ADMINISTRATION

6.1.1 STUDY INTERVENTION DESCRIPTION

The Teva Digihaler™ System consists of 4 devices. Device 1 is the ProAir® Digihaler™, which is the test IMP. The 3 investigational medical devices are: Device 2 - Patient-facing App; Device 3 - DHP (cloud solution); and Device 4 - Provider-facing dashboard. Patients will receive 2 ProAir® Digihaler™ devices at the face-to-face visits and can request additional devices if these devices have been completely used. A three-month supply of maintenance AirDuo® Digihaler™ will be provided at each in person visit and only after verification that data from the previous device has been downloaded. Patients will receive instructions for using the ProAir® Digihaler™ and AirDuo® Digihaler™ from the investigational center personnel. Patients will be instructed to return all inhalers to the investigational center at the end of treatment visit or at early termination. These devices will be brought to the in-person visits and the data download will be confirmed, after which the devices will be discarded.

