
test scores over time) in patients receiving biologic therapies.
 
Definitions: Adherence rates will be defined as: high (>80% of puffs), moderate (50-80% of puffs) and low levels (<50% of puffs) of adherence to maintenance inhalers (assuming an expected baseline usage of two puffs per day).
		
non-adherence to inhaled therapies and lead to incorrect conclusion that the biologic is not effective. In addition, little is known about how patients with severe asthma utilize their inhalers once biologics are initiated and more importantly if it is safe to discontinue these therapies altogether.

To determine the impact on inhalation parameters on categorical response to biologics. Response will be categorized as non-response, partial and complete response on the basis of six factors: a 50% reduction in exacerbations, any reduction in maintenance OCS dose, change of at least 10% in FEV1, improvement of 3 points in ACT score and patient perception of global improvement in asthma.
	
 • Proportion of patients achieving non-response, partial and complete response to biologics. 
Tests: Summary, chi-squared test, and Tukey’s HSD test statistics of inhalation parameters by response group.
	
Response to biologics is heterogeneous, and it is unclear if inhalational parameters measured by the Digihaler™ are correlated with degree of response.

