4.2 SCIENTIFIC RATIONALE FOR STUDY DESIGN

We designed an open label, single site study and intend to enroll patients in a sequential manner via screening of the EMR system for patients currently receiving biologics or with a pending approval for biologics for asthma. The open label design was selected as we are interested predominantly in inhalation parameters that are collected without any specific actions from participants, thus decreasing any potential changes in medication utilization. We intend to educate the patients on the use of the inhaler and how it has been prescribed but will make no efforts to intervene to encourage compliance with medication utilization, as we are interested in patient behavior and interaction with the device. The application that collects information about inhaler use will be stored on the patients' smart phone, and therefore they may choose to review the information and make changes in their adherence. We will not require patients to utilize the application and will passively record whether patients report using the app or not. We will design a questionnaire that determines patients' opinions of the app if they are utilizing it. All clinical parameters will be collected from the EMR.

Our main objective is to determine baseline inhalation parameters (e.g., peak inspiratory flow) using sample means. According to one study (<https://www.ncbi.nlm.nih.gov/pmc/articles/PMC5328129/>) the PIF mean was 115 and standard deviation was 15. Assuming a 100 patient sample, the 95% CI of our estimate of the PIF sample mean would be plus or minus 3, e.g., 115 (95% CI 112 – 118), which we deem to be of sufficient power for our analysis (<http://statulator.com/SampleSize/ss1M.html>).

Our secondary objective includes training a machine learning model, and one common measure to evaluate model performance is discrimination, assessed by an area under the ROC curve (AUROC). Again, assuming a 100 patient sample and a 50% event rate, we would have adequate power to conclude that a model with an AUROC performance of >0.65 has confidence intervals that won't cross 0.5 (which would be a model that is no better than chance) (<http://www.biosoft.hacettepe.edu.tr/easyROC/>).

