5 STUDY POPULATION

5.1 INCLUSION CRITERIA

1. A history of severe persistent asthma as defined by ERS/ATS criteria which includes the presence of poor asthma control on high dose ICS/LABA OR the need for high dose ICS/LABA to maintain asthma control OR oral steroids for maintenance therapy for more than 50% of the prior year.
2. Age >18 years of age or older.
3. Presence of current biologic use or planned initiation of biologics following study enrollment.
4. Patients will be categorized on the basis of asthma control (ACT < 19 will be considered poor asthma control). We will cap the patients with good asthma control at 30% and will no longer enroll those patients once the strata have been fully enrolled.
5. Willingness to switch maintenance inhalers to AirDuo® Digihaler™ and/or to use ProAir® Digihaler™ for rescue therapy. Use of nebulized albuterol will be discouraged but not prohibited. We will require patients to document nebulizer use. Patients that discontinue Pro-Air will be asked to document use of their rescue inhalers in their diaries.
6. Can read and communicate in English and is familiar with and is willing to use his/her own smart device and download and use the study application. If their smart device is not compatible with the study software; willingness to use an alternative device that will be provided by the study team.
7. Ability to provide informed consent.
8. The patient must be willing and able to comply with study requirements and restrictions and to remain at the investigational center for the required duration during the study period, and willing to return to the investigational center for the follow-up procedures and assessments as specified in this protocol.

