6.4 STUDY INTERVENTION COMPLIANCE

We will determine medication compliance by assessing the data collected from the inhaler. These inhalational parameters and medication use data will be transferred from the Digihaler™ to the patients' phone app and then to the server powering the dashboard. If a patient switches to ProAir® Digihaler™ /Airduo™ and determines that one of the inhalers is ineffective they can switch back to their original inhaler and remain in the study. The patient will need to agree to use at least one of the two digital inhalers to remain in the study (ie either the rescue or maintenance inhaler) as this will allow us to obtain the inspiratory parameters required in this study. We also ask that all non-digital inhaler use be documented in the patient diary. We will allow a maximum of 10% of the study population to switch their medications during the study.

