8.1.1.3 INTERIM PHONE CONTACT (V1, V2, V4, V5, V7, V8, V10, V11)

Patients will be contacted monthly between in person visits to assess the following:

- Review of Current Medications
- Review of Asthma Exacerbations and Healthcare Utilization
- Shipping of Inhaler (As Needed)
- Adverse Event Assessment
- Device Re-Education (As Needed)

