8.1.2.4 DIGIHALER™, TEACHING, AND ONLINE APPLICATION

Education for the appropriate use of the Digihaler™ will be provided at the Screening/Baseline visits and again as needed throughout the study. The study team will assist in registering for the digital inhaler application and periodically check to ensure data is being captured appropriately.

Inhalation parameters and number of doses will automatically be collected using the Digihaler™.

Application

The software App is a user facing software/focused smart device application for patients using the Digihaler™ product. The smart device app is used to track medication usage and allow users to self-assess their respiratory symptoms on a daily basis, share information on local environmental conditions, and produce user reports to review data over time.

The software consists of a smart device application compatible for iPhone operating systems (iOS) and Android operating systems that will store data locally on the patient's smart device. The App will receive a patient's health data automatically from the inhaler devices via Bluetooth on a smart device. The smart device camera will be used for scanning and pairing. The data will allow the patient to track their usage of medication, inhalation results, and self-assessments related to their asthma. The App will get environmental information from 1 or more web services.

TEVA Digital Health Platform

The TEVA DHP is a system that stores and transfers health data collected from the App. The cloud solution automatically synchronized with the App after events and/or at predetermined time periods/intervals. An internet connection to the smart device (e.g., wireless or cellular phone network) is required in order for communication to be established between the App and the cloud solution. The

cloud solution will not send any notifications to the App. The cloud solution does not create, modify, or delete patient information.

Patient privacy will be maintained according to the laws and regulations, and patient identifiers will be substituted to maintain a patient's privacy to reviewers of the data.

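### AirDuo resupply depends on a verified download with no stated fallback, and the adherence rate counts undownloaded, unsupplied and non-digital days as zero use

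*Combined protocol and SAP*

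**What the plan says.** All references are to the combined protocol and SAP.

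- **Supply.** Section 6.1.1 states: "A three-month supply of maintenance AirDuo® Digihaler™ will be provided at each in person visit". The same sentence then sets a release condition, under which resupply happens "only after verification that data from the previous device has been downloaded". Used devices come to the clinic visit and are discarded once their download is confirmed. Section 6.2.1 instead has empty, part-used and unused inhalers collected at study end and sent back to the sponsor or its designee.
- **Data route.** Under 6.4, inhaler data are "transferred from the Digihaler™ to the patients' phone app and then to the server powering the dashboard". Section 8.1.2.4 describes the Bluetooth link from inhaler to app and, for the step from app to cloud, says: "An internet connection to the smart device (e.g., wireless or cellular phone network) is required in order for communication to be established". No other route is described.
- **App use.** Section 4.2 says: "We will not require patients to utilize the application and will passively record whether patients report using the app or not". Inclusion criterion 6 in 5.1 asks for a patient who "is willing to use his/her own smart device and download and use the study application".
- **Phone contacts.** The schedule in 1.3 marks Digihaler dispensing at every visit from baseline to Visit 12, phone visits included, and as-needed shipping at the eight monthly phone visits. Section 8.1.1.3 repeats the shipping item. Neither mentions a download.
- **Switching.** Sections 6.4 and 7.1 let a patient go back to their own inhaler if a study inhaler is ineffective or not preferred, provided one digital inhaler is kept. Non-digital use goes in the diary.
- **Adherence.** Section 3 sets high (>80% of puffs), moderate (50-80%) and low (<50%), "assuming an expected baseline usage of two puffs per day". In 9.4.3 item 3, patients are grouped on Digihaler usage over the previous month and compared on outcomes over the next month.

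**The concern.** There are two linked gaps.

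The first is operational. Release of the maintenance inhaler rests on a check that can fail for reasons outside the patient's control, such as an unpaired phone, a lost connection or a device left at home. The sections that govern app use and supply do not agree, and none says what staff do when the check fails. Eligibility under 5.1 rests on high-dose ICS/LABA need, poor control on it, or maintenance oral steroids, so silence on this step matters.

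The second is statistical, and holds even if no supply is ever refused. A fixed denominator of two puffs per day has no place for a day on which use was not observable or not possible. Three different situations then look the same as a patient who chose not to inhale:

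- Doses taken but never downloaded. The patient was treated and is scored as untreated.
- Days on the patient's own, non-digital controller. The patient was treated, but only the diary shows it.
- Days with no study AirDuo and no other controller. This is real non-exposure, but the study caused it.

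The first two put treated patients in lower adherence groups and blur the contrast. In the third, the supply gap sets the exposure group and may also affect the next month's outcome, so the analysis would credit patient behaviour with an effect of the dispensing procedure.

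**Working it through.** The plan gives no figure on this point to reproduce, so the check is direct arithmetic on its stated rules.

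**Step 1. Size of the misclassification.** Inputs: two puffs per day and the 80% and 50% cut-points (section 3); a one-month window (9.4.3 item 3). The plan does not define the month's length, so 30 and 28 days are assumed. Let D be the days in the month, g the days scoring zero for any of the three reasons above, and a the true adherence on the other days.

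Recorded adherence = a × 2(D − g) / 2D = a × (D − g)/D.

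For a = 100% and D = 30, the expected count is 60 puffs:

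- g = 5: 50/60 = 83.3%, high.
- g = 6: 48/60 = 80.0%, not above 80%, so moderate.
- g = 15: 30/60 = 50.0%, still moderate.
- g = 16: 28/60 = 46.7%, low.

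Other cases, showing the first g at which the group changes:

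| D | True adherence | Leaves high at g | Recorded | Enters low at g | Recorded |
|---|---|---|---|---|---|
| 30 | 100% | 6 | 80.0% | 16 | 46.7% |
| 30 | 95% | 5 | 79.2% | 15 | 47.5% |
| 30 | 90% | 4 | 78.0% | 14 | 48.0% |
| 30 | 85% | 2 | 79.3% | 13 | 48.2% |
| 28 | 100% | 6 | 78.6% | 15 | 46.4% |

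A few lost days are enough to leave the high group. Reaching low takes about half a month.

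**Step 2. How much stock covers a delayed resupply.** Clinic visits are at weeks 0, 12, 24, 36 and 48 (1.3), so the nominal gap is 12 × 7 = 84 days. The ±7-day window applies at both ends, giving 70 to 98 days. The plan does not give a three-month supply in days, so 84 to 92 is assumed. Buffer = days supplied − days between visits:

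- 84 days supplied: 0 (range −14 to +14).
- 90 days supplied: +6 (range −8 to +20).
- 92 days supplied: +8 (range −6 to +22).

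At the nominal interval, stock on hand covers about a week at most. Baseline has no previous device and week 48 is the end-of-study visit, so the condition matters mainly at weeks 12, 24 and 36.

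**Step 3. The sections side by side.** The 6.1.1 condition needs the app route in 6.4 and 8.1.2.4 to have worked. Whether the patient is obliged to keep that route working depends on whether 4.2 or criterion 6 governs. Whether the condition applies outside clinic visits cannot be told from 1.3 or 8.1.1.3. Whether a device whose download failed is kept cannot be told from 6.1.1 and 6.2.1 together.

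**The case against.** The plan does more to prevent failure than the release condition alone suggests. Criterion 6 selects patients willing to use the app, and 4.2 can be read as being about engagement with the app's information rather than having it installed. Section 8.1.2.4 describes transfer as automatic, with staff helping to register the app and periodically checking capture. The check in 6.1.1 also protects data, because no device is discarded before its download is confirmed. Timestamped events are recorded on the inhaler (2.3.3, stated for ProAir), so a late download may recover doses. The shipping item in 8.1.1.3 names no product and may largely concern rescue inhalers. Shipping, monthly contact and return to the patient's own inhaler all soften a delay. Sections 6.2.1 and 10.1.9.1 refer to manuals that may hold further detail.

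All of this stands as mitigation, but none of it says what follows a failed check. Return to the patient's own inhaler is tied to ineffectiveness or preference, not to withheld supply, and 6.4 caps switching at 10% of the study population. No rule carries diary entries into the adherence rate.

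Two stronger readings are tempting and are not supported. A reader might infer that a failed download leaves the patient without controller for 12 weeks. The documents do not say supply is refused in that case, and with four-weekly contacts such a gap would need repeated failure without resolution. A reader might also infer that the resulting low adherence is simply false. That is right for doses taken but unrecorded. It is wrong for a patient who took no controller, whose exposure really was low. For the same reason, dropping unsupplied days from the denominator without further provision could label a patient untreated for half a month as high.

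**Conclusion.** The point holds in two parts.

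- **Supply.** The sections on app use, download verification, device disposal and supply at phone contacts do not fit together, and the handling of an unverified download is unstated. Interruption of study controller is a possible result of the literal wording, not a stated or demonstrated one.
- **Adherence.** Applied as written, the definition scores three kinds of non-evaluable day as zero. In a 30-day month, 6 such days move a fully adherent patient out of high and 16 move them into low. At 85% true adherence the counts are 2 and 13. This can bias the comparison in 9.4.3 item 3.

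The size of that bias cannot be computed, because the documents give no failed-download rate. If 5-10% of 100 patients had an unverified download at a visit (an assumption), that would be 5-10 downloads to resolve, not 5-10 interrupted supplies. The day counts assume a 28- or 30-day month and constant true adherence on the evaluable days. The supply buffer assumes 84 to 92 days dispensed.

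**What to change.** 1. **Reconcile** 1.3, 4.2, 5.1 criterion 6, 6.1.1, 6.2.1 and 8.1.1.3 on app use, data verification, device retention and supply, covering clinic and phone contacts. State what happens when a download cannot be verified. The supply rule itself is for the sponsor and investigator to set.
2. **Log** each failed download and keep that device until its data are recovered.
3. **Code each day** as recorded, data missing, no study supply, or non-digital controller in use (from the diary). A day covered by a successful download with no inhalation is recorded and counts as zero; a day covered by none is missing.
4. **Compute adherence over evaluable days**: puffs / (2 × evaluable days). A fully adherent patient with 16 undownloaded days of 30 then scores 28/28 = 100% instead of 28/60 = 46.7%. Set a minimum number of evaluable days before the analysis in 9.4.6, and leave months below it unclassified.
5. **Report no-supply periods as their own category**, neither as patient non-adherence nor as high adherence.
6. **Keep the plan's fixed denominator as a sensitivity analysis** for 9.4.3 item 3.

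The cost is protocol wording, one CRF field for day status, and some patient-months lost from the adherence comparison.

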6.1.2 DOSING AND ADMINISTRATION

Patients will receive the ProAir® Digihaler™ 90mcg and the AirDuo® Digihaler™ at a dose that is equivalent to the patients current inhaled therapy dose. Most patients will likely require the high dose inhaler: 232/14 device. This medication will be administered twice daily. The ProAir® Digihaler™ will be utilized up to six times per day as needed for acute asthma symptoms.

6.2 PREPARATION/HANDLING/STORAGE/ACCOUNTABILITY

6.2.1 ACQUISITION AND ACCOUNTABILITY

Each IMP shipment will include a packing slip listing the contents of the shipment, return instructions, and any applicable forms.

The research pharmacy is responsible for ensuring that deliveries of IMP for initial distribution to patients and other study materials from the sponsor are correctly received, recorded, handled, and safely and properly stored in accordance with national and local regulations, and used in accordance with this protocol.

Only patients enrolled in the study may receive IMP, and only authorized personnel at the investigational center may supply or administer IMP. All IMP must be stored in a secure, environmentally controlled, and monitored (manual or automated) area in accordance with the labeled storage conditions or appropriate instructions with access limited to the investigator and authorized personnel at the investigational center. The investigator (or designee) will instruct the patient to store the IMP according to the instructions on the label, if applicable; or will give instructions in an appropriate form. Patients will be instructed to return all IMP (empty, partially used, and unused inhalers) to the investigational center at the final visit or at early termination.

The investigator, institution, or the head of the medical institution (where applicable) is responsible for IMP accountability, reconciliation, and record maintenance (i.e., receipt, reconciliation, and final disposition records). Patients will return all inhalers at the end of the study to the investigational center for reconciliation.

A record of IMP accountability (i.e., IMP and other study materials received, used, retained, and returned) must be prepared and signed by the principal investigator or designee, with an account given for any discrepancies. All empty, partially used, and unused inhalers will be collected at the end of the study and will be returned to the sponsor or designee per sponsor instructions.

Further guidance and information are provided in the Study Reference Manual.

6.2.2 FORMULATION, APPEARANCE, PACKAGING, AND LABELING

The prescribed dose of ProAir® Digihaler™ used in this study (i.e., 90 mcg, 1 to 2 inhalations every 4 to 6 hours, as needed) was selected based on the prescribing information for PROAIR® RESPICLICK, which has the same drug delivery design as ProAir® Digihaler™. The prescribed dose of AirDuo® Digihaler™ is based on current FDA approval for the AirDuo® inhaler. The inhaler used in this study will have the digital interface for data collection, and this should not impact the drug delivery in any way. The digital inhaler is longer than the conventional inhaler but is otherwise used similarly.

Supplies of IMP will be labeled according to the current International Council for Harmonization (ICH) guidelines on Good Clinical Practice (GCP) and Good Manufacturing Practice and will include any locally required statements.

6.2.3 PRODUCT STORAGE AND STABILITY

The IMP must be stored at room temperature (15°C to 25°C [59°F to 77°F]) and not exposed to extreme heat, cold, or humidity. The investigational drug (IDS) pharmacy at the University of Michigan will be responsible for acknowledging receipt of the IMP. All study drug will be dispensed by the IDS pharmacy.

